6.9.5 Vaccine efficacy analyses

6.9.5.1 Primary vaccine efficacy analysis: HIV-1 infection

The primary analysis will be done in the PP population where participants becoming HIV infected or dropping out before the visit after the third vaccination or not having received all of the first 3 vaccinations within the specified time window or having a major specified protocol deviation, will be excluded from the analysis. The date of HIV-1 diagnosis will be the draw date of the first sample that leads to a positive test result by the diagnostic algorithm described in Section 10.3. Dropouts will be censored at the time of their last HIV-1 negative test. To evaluate the primary vaccine efficacy endpoint, the ratio of cumulative incidences of HIV-1 infection between Months 7 and 24 (vaccine vs. placebo), estimated using the transformed Nelson-Aalen cumulative hazard function estimator and tested via a Wald test. Cox proportional hazards model will also be used for estimating VE(7-24), measured by 1 minus the hazard ratio (vaccine vs. placebo) and for score testing whether the VE(7-24) differs from 0%.

As a sensitivity analysis to the primary analysis of vaccine efficacy in the PP population, targeted minimum loss-based estimation (TMLE) is used to estimate of this vaccine efficacy parameter. In particular, TMLE is used to estimate the cumulative incidences of HIV-1 infection over time for each of the vaccine and placebo groups, through to the final timepoint Month 24. These estimates will then be contrasted to estimate the primary VE parameter VE(7-24), which adjusts for covariates. This analysis has the ability to correct for bias due to measured participant covariates that predict both per-protocol status and HIV-1 infection. Iterative mean-based TMLE is used for this analysis as described in Benkeser et al. (2016, PhD dissertation). As part of the implementation of the TMLE the Super Learner is used to generate initial estimates of the conditional censoring distribution and the iterated conditional means [48]. The Super Learner library includes both parametric and nonparametric learning algorithms that are specified in the

SAP; the SAP also specifies the input variables considered by the different learning algorithms. Each learning algorithm considers adjustment for baseline demographic covariates and the baseline behavioral risk score built via supervised learning.

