of the number of primary endpoints. These cross-validation rules align with those made for the baseline behavioral risk score analysis in Moderna’s COVE trial of the mRNA-1273 vaccine.”

Date: April 5, 2022

Protocol version: 4.0 (June 12, 2020)

SAP version: 3.2

Modifications:

- In Section 8.2.2, the method used to estimate the covariate-adjusted vaccine efficacy was modified. The CFSurvival R package will now be used. In contrast to the method in the previous version of this SAP, CFSurvival does not require the discretization of time. As such, the Super Learner library in Table 2 has been modified to include survival regression methods.

Date: May 16, 2022

Protocol version: 4.0 (June 12, 2020)

SAP version: 3.3

Modifications: After the final analysis was implemented on May 2, 2022, the protocol statisticians became aware of the fact that Section 8.1 on the Primary Analysis of Vaccine Efficacy did not specify a statistical analysis of the primary parameter of per-protocol vaccine efficacy through 24 months that could be adequately justified, and therefore an update to the SAP is needed. This ascertainment is based purely on methodological grounds and is not influenced by the results.

The relevant text in the SAP v3.2 that defined the incorrect approach is as follows: “More specifically, the primary VE parameter,  $VE_{7-24}(\tau)$ , will be estimated at a fixed time point  $\tau$  chosen to be the latest possible time point when stable estimation using follow-up data through the Month 24 visit can be achieved; this is operationalized by defining  $\tau$  as the maximum time point with 150 participants in the per-protocol cohort observed to be at risk for the primary endpoint in each of the placebo and vaccine groups. All times-to-event will be right-censored at the month 24 visit.”

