### 8.2.2 Vaccine Efficacy Estimates that Adjusts for Covariates

As a supportive analysis of the hypotheses in (1), a doubly robust estimator will be used to estimate cumulative incidences of the primary efficacy endpoint over time in the per protocol population, accounting for both per-protocol and right censoring status. The estimator used for this analysis is described in Westling et al. (2021). Super Learner (van der Laan, Polley, and Hubbard, 2007; Westling, Luedtke, Gilbert, and Carone, 2021) is used to generate initial estimates of the conditional protocol violation and censoring distribution and the iterated conditional means. The Super Learner library is specified in Table 2. If any of the algorithms included in the Super Learner library return an error when run on the trial data (e.g., due to the rarity of the event), then they will be removed. Each method considers adjustment for vaccine/placebo assignment, baseline demographic covariates, and the baseline behavioral risk score built via supervised learning as described in Section 8.5. The particular demographic covariates considered are: site, country, and age at enrollment.

VE parameters will be estimated by 1 minus the ratio (vaccine group/placebo group) of the estimates of the HIV incidence probability between months 7 and 24. Influence-curve based variance estimators of each cumulative incidence are used, and the delta method is applied to obtain the variance estimator of the log cumulative incidence ratio. Point estimates and 95% pointwise and simultaneous Wald CIs for cumulative incidence curves and  $VE(t)$  curves will be plotted. For the final time point of 24 months, 2-sided Wald p-values will be reported.

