### 8.2.3 Vaccine Efficacy over Time Periods Other Than Months 0–24, Months 7–24

We will repeat the methods from Section 8.1 in the per-protocol cohort in windows other than Months 7-24. In particular, we perform these analyses in the FIS cohort, studying endpoints occurring between Month 13 and 24; and in the FIS cohort, studying endpoints occurring between Month 13 and 36. We will repeat the methods from Section 8.2.1 in the MITT cohort in windows other than Months 0–24. In particular, we perform these analyses among: MITT subjects who are HIV-1 uninfected at Month 13, studying endpoints occurring between Month 13 and 24; MITT subjects who are HIV-1 uninfected at Month 13, studying endpoints occurring between Month 13 and 36; and MITT subjects, studying endpoints occurring between Months 0 and 36.

For all analyses evaluating VE through Month 24, the failure times will be right-censored following the same approach as used for the primary analysis of vaccine efficacy. For analyses that aim to evaluate VE through Month 36, the right-censoring approach used will depend

Table 2: Models included in the Super Learner library.  $Z$  denotes vaccine/placebo assignment,  $B$  baseline behavioral risk score as described in Section 8.5, and  $W$  a vector of baseline demographic covariates. The columns indicate what type of candidate estimator was used (GLM = generalized linear model, step = stepwise GLM using both AIC and BIC as selection criteria, GAM = generalized additive model [additive Cox regression in the case of survival endpoint], RF = random survival forests, KM = Kaplan Meier) and what covariates were included ( $x * y$  indicates a cross product between covariates  $x$  and  $y$ ).

Model type	Covariates
Propensity score estimate	
GLM	$Z$
GLM	$Z + B + W$
GLM	$Z * B$
step	$Z * B + W$
Event and censoring estimates	
KM	$\emptyset$
Cox	$Z$
Cox	$Z * B$
Cox	$Z * B + W$
GAM	$Z + B$
GAM	$Z + B + W$
RF	$Z + B + W$

on the number of participants who attend their month 36 visit at the end of follow-up. The failure time convention right-censoring approach used and definition of the estimand of interest will depend on how large this number is in each of the two arms. In particular:

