## 8.5 Analysis of Exploratory Objective 3

Several analyses will make use of a baseline behavioral risk score variable. This section describes how this variable will be constructed.

Let  $Y$  denote the primary efficacy endpoint indicator (i.e.,  $Y = 1$  if the endpoint was observed and  $Y = 0$  otherwise),  $W$  a vector of demographic and behavioral risk factors collected at baseline and specified in Table 3, and  $Z$  denote a vaccine indicator ( $Z = 0, 1$  denotes placebo, vaccine). For the  $i^{\text{th}}$  participant, we define the baseline behavioral risk score as a bivariate vector  $\left(\hat{P}(Y_i = 1 \mid Z_i = 0, W_i), \hat{P}(Y_i = 1 \mid Z_i = 1, W_i)\right)$ , where we use loss-based super-learning to estimate the best model for  $P(Y = 1 \mid Z = z, W) = E_0[Y \mid Z = z, W]$ ,  $z = 0, 1$ , where  $E_0$  denotes expectation under the true data generating distribution. This is a standard prediction problem. We estimate  $E_0(Y \mid Z = z, W)$  with a minimizer of the risk of a loss:  $\psi_0 = \arg \min_{\psi} P_0 L(\psi)$ , with  $Pf \equiv \int f(o) dP(o)$ . We select binary log-likelihood loss  $L(\psi)(O) = -\{Y \log \psi(W) + (1 - Y) \log(1 - \psi(W))\}$ , given its good performance for a rare event outcome, and we stratify by  $Z$  when fitting the risk minimization problem to ensure that we are estimating  $P(Y = 1 \mid Z, W)$  rather than  $P(Y = 1 \mid W)$ . To construct an optimal estimator among any given class of candidate estimators, we use loss-based super-learning. The oracle inequality for the cross-validation selector guarantees that the estimator is asymptotically at least as good as any candidate in the set of candidate estimators. We refer to [van der Laan, Polley, and Hubbard \(2007\)](#) and [Rose and van der Laan \(2011\)](#) for details.

Let  $\hat{\Psi}_j : \mathcal{M}_{NP} \rightarrow \Psi(\mathcal{M})$  be a candidate estimator that maps an empirical distribution of  $(O_1, \dots, O_n)$  (i.e., an element of the nonparametric model  $\mathcal{M}_{NP}$  of probability distributions) into the parameter space  $\Psi(\mathcal{M}) = \{\Psi(P) : P \in \mathcal{M}\}$ ,  $j = 1, \dots, J$ . This library of candidate estimators could include a variety of parametric model based estimators as well as a variety of machine learning algorithms, possibly coupled with different dimension-reduction strategies, and possibly indexed by a variety of tuning parameters.

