Table 4 shows the combinations of prediction and screening algorithms used by the super-learner. We will plot point and 95% CI estimates of the cross-validated area-under-the-ROC curves (AUCs) ([Hubbard, Kherad-Pajouh, and van der Laan, 2016](#)) for each individual learning approach as well as for discrete super-learner and super-learner, and, for each  $z = 0, 1$ , we will separately select the learner with the lowest cross-validated AUC for finalizing the risk scores  $(\hat{P}(Y_i = 1 \mid Z_i = 0, W_i), \hat{P}(Y_i = 1 \mid Z_i = 1, W_i))$ . For each  $z = 0, 1$ , we will report the cross-validated AUC of the best model as a summary of the quality of the risk score for the given study group.

## 9 Primary Analysis to Be Conducted at the End of Stage 1

The target Month 24 visit date for the last enrolled participant is May 25, 2021, with the upper allowable limit of the visit window on June 22, 2021. Unless the trial is stopped early, the target data cut date for the end-of-Stage-1 primary analysis will be May 28, 2021.

If the trial reaches the end of Stage 1, the primary analysis report will include the following SAP-specified analyses:

1. Primary objective 1 (parts of Section 8.1)
  - (a) Estimation of month 7–24 incidence rate, with 95% CI, by treatment arm in the PP cohort

- 
- (b) Estimation of month 7–24 cumulative incidence over time by treatment arm in the PP cohort
  - (c) Estimation of month 7–24 cumulative VE over time, with 95% pointwise and simultaneous CI, in the PP cohort, with the point estimate and 95% CI for the primary VE parameter reported at time point  $\tau$
  - (d) Two-sided Wald test of  $H_0$ : month 7–24 cumulative  $VE(\tau) = 0\%$  at  $\tau$  in the PP cohort
  - (e) Estimation of month 7–24 HR VE using the Cox model, with 95% CI, in the PP cohort
  - (f) Two-sided score test of  $H_0$ : month 7–24 HR  $VE = 0\%$  in the PP cohort
2. Secondary objective 2 (parts of Section 8.2.1)
    - (a) Repeat 1(a)–(f) except for the month 0–24 period and the MITT cohort
  3. Secondary objective 3 (parts of Section 8.2.1)
    - (a) Repeat 1(a)–(c) and (e) except for the month 13–24 period and the FIS cohort
    - (b) Repeat 1(a)–(c) and (e) except for the month 13–24 period and the cohort of MITT participants uninfected at month 13
  4. Additional efficacy analyses requested by Janssen
    - (a) Repeat 1(a)–(c) and (e) except for the cohort of MITT participants uninfected at month 7

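### SAP 8.5 finalizes the behavioral risk score with the learner of lowest cross-validated AUC, which is the one that discriminates worst

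*SAP*

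**What the plan says.** SAP Section 8.5 describes how the baseline behavioral risk score is built. It opens with "Several analyses will make use of a baseline behavioral risk score variable". The super-learner is fitted by minimizing a loss ("We select binary log-likelihood loss"), separately in the vaccine and placebo arms. The cross-validated AUC is then plotted for each individual learner, the discrete super-learner and the super-learner. For each arm, "we will separately select the learner with the lowest cross-validated AUC for finalizing the risk scores". The next sentence adds that "we will report the cross-validated AUC of the best model as a summary of the quality of the risk score".

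The score is used in two places:

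- **SAP Section 8.2.2**, the supportive doubly robust analysis of the primary hypothesis. Its models adjust for treatment, site, country, age and "the baseline behavioral risk score built via supervised learning as described in Section 8.5". Table 2 labels the score B and defines it as the "baseline behavioral risk score as described in Section 8.5".
- **Protocol Section 6.9.5.1**, the TMLE sensitivity analysis: "Each learning algorithm considers adjustment for baseline demographic covariates and the baseline behavioral risk score built via supervised learning".

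**The concern.** An AUC of 0.5 means no discrimination and 1 means perfect discrimination. Choosing the lowest value therefore selects the least useful learner, while the sentence that follows reports that learner's AUC as the quality of the best model. The two sentences cannot both stand.

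The primary analysis is per-protocol, so membership of the analysis set is determined after randomization. The two adjusted analyses are the planned check on whether baseline factors linked to per-protocol status, censoring and infection distort the result. An uninformative score weakens that check and may cost precision.

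**Working it through.** The plan gives no figure to reproduce here. The check compares the wording, works out what the literal rule returns, counts how far the score reaches, and illustrates the effect by simulation.

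**1. Direction of the rule.** Section 8.5 contains two kinds of criterion. The log-likelihood loss and the cross-validated risk are to be minimized, so *lowest* would suit them. AUC is to be maximized. The sentence pairs *lowest* with AUC. No other passage defines AUC as a loss or reverses the rule. The text is current: Section 8.5 was revised in SAP v3.1, and the sentence still stands in v3.4.

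**2. What the literal rule returns.** Learner-screen pairs in Table 4, in row order: 1 + 4 + 3 + 1 + 3 + 1 + 1 = 14. Adding the discrete super-learner and the super-learner gives 16 candidates per arm.

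One of them is SL.mean, a constant within each fold. AUC = P(case scored above non-case) + ½ P(tie), so for a constant it is 0 + ½ × 1 = 0.5 in every fold that contains an endpoint. Hence the minimum over the 16 is at or below 0.5.

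If AUC is instead pooled across folds, SL.mean tends to fall lower still. With an assumed 1,000 participants per arm, unstratified 5-fold splits and 1,000 replicates, its pooled AUC averaged 0.41, 0.43 and 0.43 for 35, 50 and 65 endpoints, with a maximum of 0.50. The conclusion is the same.

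**3. Reach of the score in the SAP 8.2.2 analysis.** W is the vector of site, country and age.

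| Table 2 block | Models | Contain B | Contain W | B without W |
|---|---|---|---|---|
| Propensity | 4 | 3 | 2 | 1 (GLM Z*B) |
| Event and censoring | 7 | 5 | 3 | 2 (Cox Z*B, GAM Z+B) |
| Total | 11 | 8 | 5 | 3 |

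If B is constant, the three models with B but not W reduce to treatment only, and the models with any baseline covariate fall from 8 to 5. Table 3 lists 30 features. Three of them (site, country, age) are also in W, so 30 − 3 = 27 reach the analysis only through B.

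**4. Illustrative simulation.** The assumptions were:

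- 1,100 participants per arm. For scale, SAP v3.3 reports 969 and 1,008 per-protocol participants at risk at 24 months.
- 30 covariates, 4 of them predictive, with log odds ratios of 0.2, 0.35 or 0.5 each.
- Stratified 5-fold cross-validation, 100 replicates per setting.
- Five simplified learners standing in for Table 4.

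| Endpoints per arm | Covariates | Out-of-sample AUC, lowest rule | Out-of-sample AUC, highest rule | Difference | Constant learner picked by lowest rule |
|---|---|---|---|---|---|
| about 66 | weak | 0.523 | 0.550 | 0.027 | 55% |
| about 64 | moderate | 0.507 | 0.636 | 0.129 | 95% |
| about 61 | strong | 0.500 | 0.720 | 0.220 | 100% |
| about 33 | weak | 0.522 | 0.535 | 0.013 | 39% |
| about 32 | moderate | 0.525 | 0.603 | 0.078 | 71% |
| about 31 | strong | 0.508 | 0.689 | 0.181 | 95% |

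The literal rule gave a nearly uninformative score in every setting (0.50 to 0.53). The documents do not say how predictive the behavioral covariates are, so the gap cannot be pinned down further.

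**The case against.** The best reply is that this is an evident slip with little reach.

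- **Intent.** It can be recovered from the next sentence, and nothing suggests the literal rule was coded. That is fair, but nothing shows the opposite either, and the SAP is the prespecified record. If the code took the highest AUC, the analysis departs from the written plan; if it took the lowest, the adjusted results rest on a poor score.
- **Reach.** The itemized end-of-Stage-1 report in SAP Section 9 lists neither the Section 8.2.2 analysis nor the risk score. The key secondary MITT test in Section 8.2.1 does not use the score. The TMLE paragraph in SAP 8.1 says only that it adjusts for covariates; the score is named in the protocol. All of this stands and limits the importance of the point.
- **Worst case.** Section 8.5 defines the score as a pair, one component per arm model, so B is wholly constant only if SL.mean is selected in both arms. Treating the arms as independent, the simulated frequencies imply about 0.39² = 15% to 0.55² = 30% with weak covariates and 0.71² = 50% to 0.95² = 90% with moderate ones. The fall from 8 to 5 models is therefore conditional. No effect on the VE estimate, its bias or its interval width was calculated.
- **Detectability.** Where the loss is large, the required AUC plots would show about 0.5 beside about 0.7. This is a real safeguard, but it works only after the fact and does not correct the text.
- **Another intended wording.** *Lowest cross-validated risk* is possible. *Highest AUC* fits the following sentence better.

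**Conclusion.** The concern holds. As written, the rule selects the worst discriminator by cross-validated AUC and contradicts the sentence after it. With SL.mean in the library, the selected learner's cross-validated AUC cannot exceed 0.5. That part needs no assumption about the data beyond each fold containing an endpoint.

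The effect on results is limited and unquantified. Adjustment in the supportive analyses is weakened by an amount that depends on how predictive the behavioral covariates are, and only if the literal rule was coded. The primary VE(7-24) Nelson-Aalen estimate, its confidence interval and Wald test, interim monitoring and the Stage 2 decision are unaffected. It should be fixed, but it does not threaten the primary conclusion.

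**What to change.** Confirm the intent, then change *lowest cross-validated AUC* to *highest cross-validated AUC* in SAP Section 8.5 and record it as a dated modification. Check which rule the code applied. If it was the literal one, rerun the risk score and the covariate-adjusted analyses that depend on it, and report both sets of results.

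The change is one word, but it comes late: the SAP v3.3 entry begins "After the final analysis was implemented on May 2, 2022". That entry itself corrected the primary analysis method after the analysis had been run, so a logged late correction has precedent in this SAP. The cost is a modification entry, a code check and possibly a rerun. No new data are needed and participants are not affected.

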## 10 Trial Monitoring

The trial is monitored in four ways: (1) interim monitoring of VE for potential harm, non-efficacy, and high efficacy; (2) monitoring of the use of Truvada as PrEP; (3) monitoring for fertility to assess VE; and (4) operational monitoring for other performance standards of quality of trial conduct. Data on these monitoring activities are collated into interim reports and are presented to the independent DSMB every 6 months. Following each DSMB meeting, the DSMB reports to the Oversight Committee (OC) a summary of the trial review, which may include recommendations to modify or terminate the trial.

### 10.1 Interim Monitoring of Vaccine Efficacy for Potential Harm, Non-Efficacy, and High Efficacy

Vaccine efficacy is monitored by the independent DSMB at each DSMB meeting, with monitoring triggers based on numbers of primary HIV-1 infection endpoints (and, for non- and high efficacy, the length of completed follow-up by all on-study participants) for when the DSMB meetings begin to include formal evaluation of the potential-harm, non-efficacy, and high-efficacy stopping boundaries (these triggers are described below). The approach to sequential monitoring of VE is similar to that described in Gilbert, Grove et al. (2011). The monitoring of VE is also similar to that used for the HVTN 505 Phase 2b HIV-1 vaccine

efficacy trial ([Hammer et al., 2013](#)). The trial uses interim monitoring of VE to stop early for:

- potential harm [establish that  $VE(0-24) < 0\%$  based on a 2-sided monitoring-adjusted 90% confidence interval lying below 0%]
- non-efficacy [establish that both  $VE(0-24)$  and  $VE(7-24) < 40\%$  and  $H_0 : VE \leq 0\%$  is not rejected, based on a 2-sided 95% nominal confidence interval for VE lying below 40% and covering 0%]
- high efficacy [establish that  $VE(0-36) > 70\%$  based on a 2-sided 95% nominal confidence interval lying above 70%].

The interim monitoring for non-efficacy and high-efficacy is based on 2-sided 95% confidence intervals in order that the result of the study that would be reported in the abstract of a journal article would convey convincing evidence supporting the conclusion of non-efficacy or high efficacy. [Freidlin, Korn, and Gray \(2010\)](#) discuss a rationale for this approach to non-efficacy monitoring. The interim monitoring for potential harm is based on 2-sided 90% confidence intervals for prudence to protect the safety of study participants, i.e., less precision is required to meet a guideline for potential harm than to meet guidelines about non-efficacy or high efficacy. The interim monitoring plan is summarized in [Table 5](#).

The potential harm monitoring is done after every primary endpoint event starting at the 10th total pooled over the treatment groups, through to the time at which the non-efficacy monitoring commences. Once the non-efficacy monitoring begins, the non-efficacy monitoring serves the purpose of detecting a harmful effect of the vaccine regimen to elevate the endpoint rate compared to placebo. Details of the procedures used for the three monitoring outcomes are described next.

